### **Approach**

The study will use a two-group, pretest/posttest design. KDHRC will program the eligibility and consent forms, pretest survey and posttest surveys in Alchemer (formerly SurveyGizmo), a

secure online survey platform. This Phase I SBIR requires KDHRC to create content for two modules only: “Tooth decay impact on children and adolescents” and “Preventive oral health care.” Each module will be 20 – 30 minutes to complete and cover several expert-approved and reviewed topics. The participants in the intervention group will be sent a link to a KDHRC webpage where they will access the videos. Participants will access the videos by computer or cell phone to begin their virtual education session.

CHWs will be recruited through the CBOs and directed to an online link for eligibility screening and informed consent. KDHRC will confirm consent for each participant and after confirming consent, KDHRC will randomize each participant with completed consent into the treatment or control group using a 1:1 randomization. KDHRC will alternate assigning each participant with completed consent to the treatment group or the control group. Then, KDHRC will send each participant the link to the online pretest survey. After completing the pretest survey, each treatment group participant will receive access to a virtual education session with two GRIN modules. The control group will not receive an intervention. Each participant will receive the posttest survey two weeks after completing the pretest survey.

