### **Participants and recruitment**

CBOs with signed contracts to participate in the study will designate a POC who will be responsible for sharing recruitment materials with potential participants at their respective CBO. KDHRC will require each CBO to participate in a kick-off call with KDHRC staff during which time KDHRC staff will review the study protocol and answer additional questions. After the call, each CBO will be required to sign and return the certification form (see **Attachment X**) that states that the CBO POC understands the process and will follow the procedures outlined during the kick-off call. KDHRC will send the certification form via email or DocuSign to the CBO POC to sign prior to the CBO receiving the recruitment materials. If the CBO POC fails to follow the provisions of the certification form, the CBO will be removed from the study and will not receive full compensation.

CBOs will recruit potential participants in their networks, including potential participants within their CBOs, by sharing KDHRC-developed and IRB-approved recruitment materials (e.g., email template, flyer) thru email (e.g., listservs) and message boards. The recruitment materials will contain the link to the eligibility form, information on the time commitment, and instructions to contact KDHRC with questions. The study will include up to 120 CHWs nationwide (60 treatment, 60 control) from up to 16 CBOs. Although CBOs will recruit participants and may have access to potential participant information (e.g., name, email address) from their listservs, CBOs will not have knowledge of who actually serves as study participants and will not have access to enrolled participants’ data. KDHRC will remind participants that participation in the study is completely voluntary, that the CBO that shared recruitment materials with the participant will not have knowledge of who actually serves as study participants, and that his or her participation is no way tied to his or her position at and/or relationship with the CBO that shared recruitment materials with him or her.

Eligibility criteria for CHWs include:

- Must be at least 18 years old
- Must self-identify as a community health worker

- Must conduct outreach to Black clients

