## **Methods**

Upon completing and submitting the consent form to participate, each participant will be randomly assigned to either the treatment group or the control group. Then, KDHRC will send each participant the link to the online pretest survey. Participants will have two weeks to complete the pretest survey. A KDHRC researcher will send approximately three reminders (email, phone, text) per week to each consented participant to complete the pretest survey.

KDHRC will email the treatment group participants the information to access a virtual education session. When each participant accesses the virtual education session for the first time, each participant will be prompted to create a user ID and password and provide the last two letters of his or her last name, his or her three letter initials, and his or her year of birth, to access the virtual education session. Participants in the treatment group will have two weeks to complete the virtual education session. Participants in the control group will not receive an intervention for the two weeks between surveys. KDHRC will send one reminder (email or phone) per week to participants to promote continued engagement with the study (e.g., remind treatment participants to complete the virtual education session; remind control participants of the date when they will receive their posttest survey).

Then, two-weeks after pretest completion, KDHRC will email all participants the links and instructions for posttest survey completion. Each participant will have two weeks to complete the posttest survey. A KDHRC researcher will send approximately three reminders (email, phone, text) per week to each consented participant to complete the posttest survey.

The links to the pretest and posttest surveys will be used to collect participant data, therefore only KDHRC staff will have access to raw data. Each survey will take no more than 45 minutes to complete.

---

 We provide an additional incentive for treatment participants because treatment participants will access a virtual education session with two GRIN modules while the control group does not have to access anything.

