#### Power estimate and effect size

We computed power for multiple regression based on the designated outcomes, a single measure of treatment exposure, dosage of the exposure, and demographics modeled as control measures. Table 1 shows the results of simulation models for continuous outcomes, which varied the values of  $R^2$  for the multivariate regression, the treatment measure's contribution to  $R^2$ , and the total number of predictors in the model.

We estimated power at .80, assuming each outcome measure will have the same range of explained variance, and produced a range of sample sizes under the following conditions:

- The probability of the outcome (target achieved) for the treated under the null hypothesis ( $p_1$ ) and under the alternative hypothesis ( $p_2$ ), with  $p_1 + p_2 = 1$ . Three pairs of probabilities will be used, with the constraint that  $p_1 < p_2$ .
- $R^2$  other than X, that is, the proportion of variance explained by predictors other than the treatment (the same values set for multiple linear regression were used).
- The distribution and  $\pi$  parameter of the treatment variable: binomial and the parameter 0.5 (same probability of being a case or a control).

Because varying the number of predictors had little influence on the simulation, we used six predictors with multiple linear regression. As Table 2 shows, increasing the effect size reduces the required sample size. Power for dichotomous outcomes using multivariate logistic regression required slightly larger sample sizes.

Therefore, with a medium  $R^2$  value (.30) and contribution of treatment <.30, the estimated sample size for power = 0.80 is 36 (range 23-59). Our planned sample size of 60 participants per condition will give us adequate power and allow for attrition.

Table 1. Power estimates for continuous outcomes				
$R^2$	Contribution of treatment to $R^2$	Estimated effect size	Estimated sample size for power = 0.80	Range of est. sample size for power = 0.60-0.95
0.30	0.02	0.071	112	74-184
0.30	0.05	0.200	42	28-68
0.30	0.10	0.500	19	14-29
0.40	0.02	0.053	152	96-249
0.40	0.05	0.143	58	37-94
0.40	0.10	0.333	27	18-42
0.50	0.02	0.042	191	120-314
0.50	0.05	0.111	73	47-119
0.50	0.10	0.250	34	23-55

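### The plan states no step that would refuse, discourage or detect a control CHW opening the GRIN modules through a forwarded link, so any dilution of the contrast would go unmeasured

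*Protocol*

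**What the plan says.** **Access.** The Protocol (Approach) says of the intervention group that they "will be sent a link to a KDHRC webpage where they will access the videos". Methods adds: "KDHRC will email the treatment group participants the information to access a virtual education session". At first use "each participant will be prompted to create a user ID and password and provide the last two letters of his or her last name", and also gives initials and year of birth. The Identifying Information section builds the survey ID from these same elements.

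**Assignment.** Approach: "KDHRC will alternate assigning each participant with completed consent to the treatment group or the control group". The unit is the individual CHW, not the CBO.

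**Recruitment.** Participants and recruitment: "The study will include up to 120 CHWs nationwide (60 treatment, 60 control) from up to 16 CBOs". CBOs recruit from their wider networks and from their own staff, by email lists and message boards. Under Responsible Parties, each CBO must have at least 15 active CHWs.

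**Comparator.** Approach: "The control group will not receive an intervention".

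**Analysis.** The SAP's sample-size text mentions room for attrition only. It names a dosage term among the model inputs, but does not define it or say that it is measured in controls.

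Neither document mentions a check of module registrations against the allocation list, a request not to share the link, or any reporting of controls who entered the modules.

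**The concern.** The study question is how far GRIN raises knowledge, attitudes and beliefs, self-efficacy and intentions. The answer is the difference between CHWs who were given the modules and CHWs who were not. A control CHW who completed the modules before the posttest would tend to raise the control mean and pull that difference toward zero.

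The setting makes sharing plausible. The material is useful to any CHW, it opens from a web link, users make their own credentials, and treatment and control CHWs may be colleagues or belong to the same listserv.

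The estimate is meant to inform the Phase II trial. If it were diluted by an unknown amount, nobody could correct or even describe the dilution, although the login already collects what would be needed to see it.

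**Working it through.** **1. Do the arms share CBOs?** If all 16 CBOs take part and contribute equally, 120/16 = 7.5 CHWs per CBO, or about 4 per arm. Fewer CBOs would mean more from each. With alternating individual assignment, most CBOs would have CHWs in both arms. This is an inference; the documents do not state it.

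**2. Inputs for the power check.** From the SAP: six predictors, N = 120, and the Table 1 effect sizes. Assumed: two-sided α = .05, because the SAP states neither α nor sidedness. Also assumed: the contaminated fraction c, shown from 5% to 30%, because the documents give no rate.

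**3. Reproducing Table 1.** Write t for the treatment contribution. The tabled effect sizes follow f² = t/(R² − t):
- R² = .30, t = .02: .02/.28 = .071
- R² = .30, t = .05: .05/.25 = .200

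Power for one coefficient comes from the noncentral F distribution with 1 and N − 7 degrees of freedom and λ = N·f². This gives N = 112 and N = 42 for these two rows at power .80, as tabled. All nine tabled sample sizes at power .80 reproduce. The SAP's headline N of 36 matches no Table 1 row; an f² of about .234 gives 36.

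**4. Effect of contamination on the estimate.** If a fraction c of controls receive the full effect Δ, the control mean rises by cΔ. The arm difference becomes Δ − cΔ = (1 − c)Δ. At c = 10% (6 of 60 controls), the estimate is 10% too small, whatever the sample size. Partial exposure gives less.

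**5. Effect on power at N = 120.** The effect size becomes about f²(1 − c)², so λ = 120·f²·(1 − c)². The small rise in control-arm variance from mixing is ignored. Examples:
- f² = .02/.28, c = 10%: λ falls from 8.57 to 8.57 × .81 = 6.94
- f² = .200, c = 30%: λ falls from 24.0 to 24.0 × .49 = 11.76

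| c | f² = .071 (R² .30, t .02) | f² = .200 (R² .30, t .05) | f² ≈ .234 (implied by headline N = 36) |
|---|---|---|---|
| 0 | .827 | .998 | 1.000 |
| 5% | .787 | .996 | .999 |
| 10% | .743 | .992 | .997 |
| 20% | .641 | .973 | .988 |
| 30% | .529 | .925 | .957 |

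The power loss is material only in the first column. There, 10% contamination costs .827 − .743 = .084.

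**The case against.** **Silence is not proof of an open door.** Access details are emailed to the treatment group only, which is a real if partial safeguard. The login also asks for the elements of the study ID, so the page may well check them. A reader might infer that control CHWs can view GRIN and that the comparator is unprotected. The documents do not go that far: no protection beyond the targeted email is stated, and none is ruled out.

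**The sizing does not assume zero contamination.** A reader might take the SAP's parameter of 0.5 for the treatment variable as an assumption that arm equals exposure. It is only an allocation ratio. The SAP makes no allowance for contamination, which is a weaker statement. Its dosage term also shows that exposure was considered, although the term is undefined.

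**The sample size has room.** At f² = .200 and the planned 120, 10% contamination costs less than one point of power. This stands, and it rules out a general claim that the study would be underpowered.

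**Full exposure is the worst case.** A control would have to obtain the link, register and work through two modules of 20–30 minutes each. The extra $25 for completing them is offered only to treatment CHWs. The true rate could be near zero.

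**Shared workplaces are inferred.** CBOs recruit through national networks as well as in-house, social media may be added, and CBOs are not told who takes part.

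All five points stand as limits on size and likelihood. None supplies a step that would stop, or reveal, a control CHW using a forwarded link.

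**Conclusion.** The concern holds in a limited form. The documents combine link-based access with self-created credentials and individual assignment within shared recruitment networks, and they state no way to refuse, discourage or detect control access. The supportable harm is a shrinkage of the effect estimate, of unmeasured size: by c if a fraction c of controls receive the full effect, and by less with partial exposure.

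Power is secondary. At N = 120 it remains at least .92 for c up to 30% at f² = .200, and drops below .80 only near the smallest R² = .30 effect (.827 to .743 at c = 10%). These figures rest on the assumed c, a two-sided α of .05, Table 1's own effect sizes and no attrition.

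A reader might also conclude that a null result could not be attributed to GRIN. That does not follow: in this model, 10% to 30% contamination shrinks a real effect by 10% to 30% and does not abolish it. The point is worth acting on because the remedy costs little, not because the design fails.

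**What to change.** **Protocol, Approach and Methods.** Accept a module registration only when the entered ID elements match the treatment list, or when the user supplies a code sent to treatment CHWs. In the access email, ask treatment CHWs not to share the link until data collection ends.

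**SAP, Statistical methods for outcome measures.** Compare module-login IDs with control survey IDs and report the number of control CHWs who entered the modules. Keep them in the arm assigned, and note that the estimate is diluted if that number is above zero.

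**Cost.** A small change to a login page the sponsor is already building, one sentence in an email and a short addition to the SAP. No new data items or participants are needed, because the login and the survey gateway already use the same ID elements. The downside is occasional help for treatment CHWs whose entries do not match or who mislay the code.

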## **Analysis**

KDHRC will program the eligibility and consent forms, pretest survey, and posttest surveys in Alchemer, a secure online survey platform. After completion of the study, KDHRC will download the raw data from Alchemer into encrypted Excel spreadsheets.

KDHRC will import the data into STATA, a quantitative statistical software, to analyze and assess the extent to which the GRIN prototype increases CHWs' knowledge, attitudes and beliefs, perceived self-efficacy, and intentions to conduct oral health care outreach to low-income Black guardians.

## **Timeline**

The study will begin immediately upon obtaining IRB approval. All data collection will conclude by June 30, 2022.

## **DATA COLLECTION**

KDHRC will collect quantitative data from up to 120 CHWs (60 CHWs per group) through online surveys only. If KDHRC encounters low recruitment numbers and/or high attrition rates, then KDHRC will contract with additional CBOs and utilize additional recruitment methods (e.g., social media) to reach additional participants. This will not impact the rights of or risk to study participants.

## **Identifying Information**

CBOs will not have access to enrolled participants' survey responses. Although CBOs will recruit participants and may have access to potential participant information (e.g., name, email address) from their listservs, CBOs will not have knowledge of who actually serves as study participants and will not have access to enrolled participants' data.

KDHRC will not share consented participants' names or contact information with CBOs. KDHRC will collect participants' names, email addresses, and phone numbers to share study information and send reminders. KDHRC will not link names or other identifying information to the responses. Each participant will create an ID number based on several survey questions (last two letters of his or her last name, his or her three letter initials, and his or her year of birth). KDHRC will collect this information solely to match participant data.

KDHRC will use an Alchemer-developed system to match each participant's pretest and posttest survey responses using URL redirects and a "gateway survey." When participants click the KDHRC-provided link to access the pretest survey, participants will first be directed to a separate page (the "gateway survey") where they will be prompted to enter their ID number and select that they need to complete the pretest survey. The participant will then automatically be redirected to the pretest survey questions. After the two-week intervention period, KDHRC will email participants the same link that directs participants to the "gateway survey." Participants will enter the same ID number and select that they have already completed the pretest survey two weeks prior. Participants will automatically be redirected to the posttest survey questions. Alchemer, the secure online survey platform, will automatically match each participant's pretest and posttest survey question responses and create one composite complete, matched pretest and

---

 [Create a Pre-Test and Post-Test Survey | Alchemer Help](#)

posttest dataset per participant. Although each participant's ID number will be collected in the back end of the online survey platform, participants will not enter their ID number on the pretest survey questions or the posttest survey questions. Full names will not be recorded on surveys and participants will not provide other identifying information to researchers through the surveys.

KDHRC will save all raw data on KDHRC's secure server in a project specific, password protected folder. KDHRC will destroy all raw data and related forms one year after the end of data analysis.

#### **Assurance of Confidentiality**

Confidentiality is crucial to the protection of human subjects. Therefore, KDHRC will strictly follow its established procedures on the protection of confidential information. Moreover, all KDHRC staff who have access to these data will sign confidentiality pledges. Only links to the pretest and posttest surveys will be used to collect participant data, therefore only KDHRC staff will have access to raw data. KDHRC will keep information that participants provide private and confidential. KDHRC will offer to share the research report with CBOs at the conclusion of the study. KDHRC will inform participants prior to their participation that their responses are confidential. KDHRC will also advise participants of the nature of the activity, the length of time it will require, and that participation is purely voluntary and that they can stop at any time. KDHRC will assure participants that no penalties will occur if they wish not to respond, either to the information collected as a whole or to specific questions.

As a further confidentiality guarantee, KDHRC will present data in reports in aggregate form only and will not preserve links to individuals. KDHRC will track consent electronically and collect data through Alchemer, the online platform that is only accessible with the KDHRC username and password. Further, KDHRC will store participant responses in a password-protected files on the KDHRC server.

**Guardians Receiving Information through Navigators (GRIN)**  
**Statistical analysis plan**  
**NCT05511935**  
**September, 4 2020**

## GRIN Phase I feasibility study

### Statistical design and power

#### Number of subjects

We will enroll 60 participants per group, for a total of 120 participants.

#### Power estimate and effect size

We computed power for multiple regression based on the designated outcomes, a single measure of treatment exposure, dosage of the exposure, and demographics modeled as control measures. Table 1 shows the results of simulation models for continuous outcomes, which varied the values of  $R^2$  for the multivariate regression, the treatment measure's contribution to  $R^2$ , and the total number of predictors in the model.

We estimated power at .80, assuming each outcome measure will have the same range of explained variance, and produced a range of sample sizes under the following conditions:

- The probability of the outcome (target achieved) for the treated under the null hypothesis ( $p_1$ ) and under the alternative hypothesis ( $p_2$ ), with  $p_1 + p_2 = 1$ . Three pairs of probabilities will be used, with the constraint that  $p_1 < p_2$ .
- $R^2$  other than X, that is, the proportion of variance explained by predictors other than the treatment (the same values set for multiple linear regression were used).
- The distribution and  $\pi$  parameter of the treatment variable: binomial and the parameter 0.5 (same probability of being a case or a control).

Because varying the number of predictors had little influence on the simulation, we used six predictors with multiple linear regression. As Table 2 shows, increasing the effect size reduces the required sample size. Power for dichotomous outcomes using multivariate logistic regression required slightly larger sample sizes.

Therefore, with a medium  $R^2$  value (.30) and contribution of treatment <.30, the estimated sample size for power = 0.80 is 36 (range 23-59). Our planned sample size of 60 participants per condition will give us adequate power and allow for attrition.

Table 1. Power estimates for continuous outcomes				
$R^2$	Contribution of treatment to $R^2$	Estimated effect size	Estimated sample size for power = 0.80	Range of est. sample size for power = 0.60-0.95
0.30	0.02	0.071	112	74-184
0.30	0.05	0.200	42	28-68
0.30	0.10	0.500	19	14-29
0.40	0.02	0.053	152	96-249
0.40	0.05	0.143	58	37-94
0.40	0.10	0.333	27	18-42
0.50	0.02	0.042	191	120-314
0.50	0.05	0.111	73	47-119
0.50	0.10	0.250	34	23-55

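### Table 1 divides the treatment's contribution by the wrong variance, so the R² = .30 sample sizes are too small by a factor of about 2.5 to 3

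*SAP*

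**What the plan says.** The SAP section on power and effect size describes a multiple regression calculation: "Table 1 shows the results of simulation models for continuous outcomes, which varied the values of" three inputs, namely the model's R², how much of it treatment adds, and how many predictors there are. Because the number of predictors mattered little, "we used six predictors with multiple linear regression". The target is given as "We estimated power at .80, assuming each outcome measure will have the same range of explained variance"; no alpha or sidedness is stated.

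Table 1 covers R² = .30, .40 and .50, crossed with treatment contributions of .02, .05 and .10. Its first two rows (R², contribution, effect size, N for 80% power, N range for 60% to 95% power) read "0.30 0.02 0.071 112 74-184" and "0.30 0.05 0.200 42 28-68". The third R² = .30 row gives effect size 0.500 and N 19 (14-29).

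The text then takes R² = .30 as a medium value, gives a required sample of 36 (23-59), and concludes: "Our planned sample size of 60 participants per condition will give us adequate power and allow for attrition".

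**The concern.** The direction of the table is wrong. For a fixed treatment contribution, a model that explains more of the outcome leaves less residual variance, so fewer participants should be needed. Table 1 shows the opposite: at a contribution of .02 the N goes from 112 to 152 to 191 as R² goes from .30 to .40 to .50. That suggests the effect size was built on explained rather than unexplained variance.

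Table 1 is the only power table the SAP prints, and both the choice of 60 per group and the statement about attrition lean on it. If its R² = .30 rows are too optimistic, the study could miss modest effects while being described as adequately powered. The Protocol (Purpose of Research) says the results will inform a later randomized trial, so a null finding could be over-read.

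**Working it through.** **Inputs.** From the SAP: six predictors, power .80, the nine combinations of R² and contribution c, and a total N of 120 (60 per group). Assumed: two-sided alpha .05, and 20% attrition for illustration (96 completers), because the documents give no rate.

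**Method.** F test of one regression coefficient: numerator df 1, denominator df N − 7, noncentrality f² × N.

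**Step 1: how the printed effect sizes arise.** All nine equal c/(R² − c):
- R² = .30: .02/.28 = .071; .05/.25 = .200; .10/.20 = .500
- R² = .40: .02/.38 = .053; .05/.35 = .143; .10/.30 = .333
- R² = .50: .02/.48 = .042; .05/.45 = .111; .10/.40 = .250

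The denominator R² − c is the variance explained by the other predictors.

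**Step 2: reproduce the printed Ns.** With these unrounded effect sizes the test gives 112, 42, 19, 152, 58, 27, 191, 73 and 34. All nine match exactly. Of the 18 range limits, 17 match; the exception is the printed 74, which computes as 71. One-sided alpha .05 gives 89, 33 and 15 for the R² = .30 rows, so two-sided .05 is the level that fits.

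**Step 3: correct the denominator.** Use f² = c/(1 − R²). At R² = .30: .02/.70 = .0286; .05/.70 = .0714; .10/.70 = .1429.

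| R² | c | Printed N | Corrected N | Ratio | Power at N = 120 | Power at N = 96 |
|---|---|---|---|---|---|---|
| .30 | .02 | 112 | 277 | 2.47 | 45% | 37% |
| .30 | .05 | 42 | 112 | 2.67 | 83% | 74% |
| .30 | .10 | 19 | 58 | 3.05 | 98% | 96% |
| .40 | .02 | 152 | 238 | 1.57 | 51% | 43% |
| .40 | .05 | 58 | 97 | 1.67 | 88% | 80% |
| .40 | .10 | 27 | 50 | 1.85 | 99% | 98% |
| .50 | .02 | 191 | 199 | 1.04 | 58% | 49% |
| .50 | .05 | 73 | 81 | 1.11 | 93% | 87% |
| .50 | .10 | 34 | 42 | 1.24 | >99% | 99% |

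The corrected N now falls as R² rises (277, 238, 199 at c = .02). At the printed Ns for R² = .30, true power is 43%, 39% and 33%, not 80%.

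**Step 4: try the other reading of R².** One of the SAP's listed conditions defines R² as the share explained by the covariates without treatment. Then f² = c/(1 − R² − c), and the R² = .30 rows need 269, 105 and 50, still 2.4 to 2.6 times the printed values. This reading agrees with the table only at R² = .50, where R² and 1 − R² are the same number. Put another way, the printed R² = .30 rows answer the question for a model whose other predictors explain 70%.

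**Step 5: what 120 participants deliver.** The smallest f² detectable with 80% power is .0665 at N = 120 and .0836 at N = 96. At R² = .30 these are contributions of .0665 × .70 = .047 and .0836 × .70 = .059.

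**The case against.** The formula error cannot be explained away, but its consequence can be argued down.

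- **The summary figure may not come from the R² = .30 rows.** No such row prints 36 (23-59). Halving the R² = .50, c = .05 row, 73 (47-119), gives 36.5 (23.5-59.5), which rounds down to exactly those numbers. If it is a per-group figure from that row, the corrected value is 81 in total, about 41 per group, still under 60. This is a plausible inference and it stands as such. It does not rescue the text, which names R² = .30 as the basis. It would mean the summary also carries the wrong R² label.
- **Few cells change their answer at N = 120.** Seven of nine printed cells need 120 or fewer, and six of nine do after correction. Only R² = .30, c = .02 crosses over. The printed table already showed 152 and 191 for the other two .02 rows. This is correct. What the count hides is the lost margin at R² = .30, c = .05: 120 against 42 becomes 120 against 112.
- **The 20% attrition is assumed, and the Protocol allows further recruitment.** Both are true: Data Collection provides for more community organizations and other recruitment methods if attrition is high. But the SAP claims an allowance for attrition without stating a rate, and at R² = .30, c = .05 that allowance is 8 participants (8/120, about 7%).
- **This is a feasibility study, and no procedure changes.** That is why enrolment can stay as it is. It does not justify leaving incorrect power figures in the plan.

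**Conclusion.** The concern holds. Table 1 uses contribution/(R² − contribution) where contribution/(1 − R²) is required, and its Ns were computed from those values. At R² = .30, the value the SAP's conclusion names, the required Ns are understated by a factor of 2.47 to 3.05. The error is smaller at R² = .40 (1.57 to 1.85) and slight at R² = .50 (1.04 to 1.24).

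With 120 participants, a contribution of .02 does not reach 80% power at any listed R². At R² = .30, a contribution of .05 reaches it with almost no room for attrition, and .10 is comfortably covered. The unqualified statement of adequate power with attrition allowed for should not stand.

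The sample sizes rest on two-sided alpha .05, which is inferred because it reproduces the printed Ns. The denominator error does not depend on alpha. The figures at 96 completers rest on the assumed 20% attrition.

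**What to change.** 1. Recompute Table 1 with effect size = contribution/(1 − R²), including the range column. State whether R² is the full model's value or that of the covariates alone, and use the matching denominator (1 − R² − contribution for covariates alone). State alpha and sidedness.
2. Replace the 36 (23-59) summary with figures traceable to a row of the corrected table, and say whether each is a total or per group.
3. Replace the closing power claim with what 120 participants deliver at R² = .30: 80% power for a treatment contribution of about .047 with no attrition and about .059 with 20% attrition (labelled as assumed), and 45% power for a contribution of .02. Make no claim of adequate power for effects smaller than those detectable.

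The cost is one table and one paragraph of the SAP, and a less favourable power statement. Enrolment and study procedures do not change.
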